### 7.3.3. Confounders and Effect Modifiers

Standard variables to be evaluated and included at the index date:

#### Demographic variables at index

- Age (years, also categorized as 18-49, 50-64,  $\geq 65$  years)
- Sex assigned at birth (female, male)
- Gender identity
- Race
- Ethnicity
- Marital status (single, married/domestic partner, widowed, separated/divorced, unknown)
- Geographic region
- Route of HIV infection (men who have sex with men, people who inject drugs, heterosexual, vertical, Other)
- Payer type (Medicaid, Medicare, commercial insurance, AIDS Drug Assistance Programs/Ryan White, cash)

#### Virologic variables at regimen initiation

- HIV VL at initiation of CAB+RPV LA regimen
  - Continuous (copies/mL)
  - Categorical:
    - $< 50$  copies/mL (or  $<$  limit of detection in clinics where limit of detection  $> 50$  copies/mL)
    - $\geq 50$  to  $< 200$  copies/mL
    - $\geq 200$  to  $< 1,000$  copies/mL
    - $\geq 1,000$  to  $< 10,000$  copies/mL
    - $\geq 10,000$  to  $< 100,000$  copies/mL
    - $\geq 100,000$  copies/mL
    - Missing
- Type of VL assay
  - Abbott RealTime
  - Aptima Quant Dx
  - Roche 6800

- Roche Cobas

**Immunologic variables at regimen initiation**

- CD4 cell count at initiation of CAB+RPV LA regimen
  - Continuous (cells/ $\mu$ L)
  - Categorical:
    - $> 500$  cells/ $\mu$ L
    - $> 350$  to  $\leq 500$  cells/ $\mu$ L
    - $> 200$  to  $\leq 350$  cells/ $\mu$ L
    - $> 50$  to  $\leq 200$  cells/ $\mu$ L)
    - $\leq 50$  cells/ $\mu$ L
    - Missing
- CD4/CD8 ratio
- CD4 nadir prior to initiation of CAB+RPV LA

**Clinical variables at regimen initiation**

- Number of years since HIV diagnosis
- Number of years since first ART initiation
- HIV subtype where available
- History of previous ARV exposure before CAB+RPV LA
  - Number of core agents experienced
  - Number of ARV classes experienced
  - Duration of last ARV regimen
  - Prior core agent class
- History of previous virologic failure
- History of previous HIV drug resistance and any historical HIV-1 subtype information, where available
- BMI, height, weight
- History of AIDS-defining events
- Veterans Aging Cohort Study (VACS) Mortality Index score
  - Characteristics for mortality index calculation include age, CD4 count, HIV-1 RNA level, Hemoglobin, FIB-4 index, eGFR, HCV status, albumin, BMI, white blood cell count
- ASCVD risk score
  - Characteristics for CVD risk calculation include age, sex, race, total, LDL and HDL cholesterol, systolic and diastolic blood pressure, on

antihypertensive therapy, on a statin, on aspirin therapy, history of diabetes, and smoking status.

- Framingham risk score
  - Characteristics for CVD risk calculation include age, sex, total and high-density lipoprotein cholesterol, systolic blood pressure, antihypertensive therapy, and smoking status.
- Co-infections
  - Hepatitis B co-infection including serology status
  - Hepatitis C co-infection
  - Syphilis infection (ever)
- Comorbidities
  - Autoimmune disease
  - Cardiovascular disease
  - Invasive cancer
  - Endocrine disorder
  - Mental health disorder
    - Depression
    - Anxiety
    - Sleeplessness
    - Suicidality
  - Liver disease
  - Bone disorder
  - Peripheral neuropathy
  - Renal disease
  - Hypertension
  - Substance abuse
  - Non-AIDS–defining malignancies (excluding hepatocellular carcinoma)
  - Any of the above
- Concomitant medications
  - Anticonvulsants
    - Carbamazepine
    - Oxcarbazepine
    - Phenobarbital
    - Phenytoin
  - Antimycobacterials

- Rifampin
- Rifapentine
- Rifabutin
- Glucocorticoids
  - Dexamethasone
- Macrolide or ketolide antibiotics
  - Azithromycin
  - Clarithromycin
  - Erythromycin
- Narcotic analgesic
  - Methadone

#### 7.4. Data Sources

- **Participant surveys:** Prospective participants of CAB+RPV LA will be asked to complete an online survey at enrollment, at month 12 (if applicable), and if they discontinue CAB+RPV LA. The baseline survey will be administered prior to the first CAB+RPV LA injection. The online survey will include the WHOQOL-HIV BREF, the HIVTSQs, and the HIVTSQc (O’Connell, 2012; Woodcock and Bradley, 2001; Woodcock and Bradley, 2006) and several bespoke questionnaires developed for this study. Appropriate agreements with the copyright owners will be in place for use in this study. It is estimated that the participant surveys will take approximately 20 minutes to complete.
- **Participant medical information via site-completed eCRF:** The investigator or authorized medical staff will record clinical and treatment data from participants’ medical records into an eCRF at enrollment, minimum of two annual follow-ups (unless participant discontinued CAB+RPV LA) and at study end.

Participant surveys and medical record information will be linked by a common participant identifier (ID) code that will be retained by the site.

#### 7.5. Study Size

The study will aim to enroll up to approximately 2,000 participants. Among them, it is estimated that 250 participants are already receiving CAB+RPV LA at the time of study start, and 1,750 participants will be newly initiating CAB+RPV LA.

There is no formal statistical hypothesis to be tested in these analyses. The study will be descriptive in nature and will focus on absolute effectiveness estimation. A precision calculation was performed using power analysis and sample size (PASS) software version 14 using the exact Clopper-Pearson method based on the cumulative probabilities of the binomial distribution for 1 proportion.

In order to demonstrate the estimated precision for the total sample size and also among the groups of participants already receiving and newly initiating CAB+RPV LA, Table 1 presents the precision calculations for the width of 95% confidence intervals for a range of proportions and a combination of sample sizes. It is anticipated that data from 2,000

participants are thought adequate to provide reasonable precision around a point estimate (here defined as a proportion) to meet the study objectives. With 2,000 participants, the 2-sided 95% confidence interval precision width for the estimation of virologic failure rate will range from 1.28% and 2.13% for a failure rate ranging from 2% to 6%.

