## 7. RESEARCH METHODS

### 7.1. Study Design

This is a non-interventional prospective observational cohort study using data from individual medical records, assessments from participating clinical sites, and participant-reported data from electronic questionnaires. Prospective participants will be followed from the date of their first CAB+RPV injection for a minimum of two years, unless they withdraw from the study, are lost to follow-up, or pass away. Participants that discontinue CAB+RPV LA and switch to a different ART regimen or to monthly CAB+RPV LA dosing schedule or experience CVF, will continue to be followed to describe virologic response and treatment switching. Retrospective participants will be included in the study regardless of whether they are still on CAB+RPV at the time of the study start and will have all applicable data collected. Participants who are deceased or lost to follow up will not be included.

For this non-interventional study, treatment and laboratory testing decisions will be made by the treating physician according to standard practice, taking into account the treatment history, individual characteristics, the approved prescribing information or summary of

[figure not shown]
product characteristics for CAB+RPV LA formulation, contemporary regimen and local guideline or recommendations. Testing for resistance and subtype at discontinuation/virologic failure will be part of the standard of care at selected sites, and the study will include only the clinical sites that conduct resistance and subtype testing as standard of care. The study protocol will be implemented by RTI Health Solutions (RTI-HS).

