**Retrospective Participants:**

Retrospective participants will include individuals who initiated CAB+RPV LA from January 2023 and will be followed for up to two years. Participants who have discontinued CAB+RPV LA for any reason will be included and participants who are deceased or lost to follow up will not be included. Participants who discontinue and switch to a subsequent regimen or who experience CVF will be followed-up for a minimum of 6 months and may be extended until viral load assessment is completed, with a maximum duration of 12 months.

The sampling methodology will be designed with the goal of maximising the probability that each individual treated with CAB+RPV LA will have an equal opportunity to be selected. Participants will be enrolled as they come in for a scheduled visit, however if the volume of participants at a site is large, a customized, site-specific sampling approach may be devised to achieve an efficient method of obtaining a representative sample of participants. In some sites, it is likely that all treated participants will be selected.

The study will aim to select a diverse group of medical practices to represent diversity in clinical practice settings and to support recruitment of a diverse sample of participants (e.g., prioritizing non-cisgender males, individuals aged 50 years or older, and individuals with BMI  $\geq 30$  kg/m^2).

Individuals who are viremic (VL  $\geq 50$  copies/mL) at initiation will not be included in this study. Individuals with VL results available around the time of initiation at VL  $< 50$  copies/mL will be included in the study regardless of VL levels following enrollment.

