## 7.7. Data Analysis

### 7.7.1. Primary Analysis

#### 7.7.1.1. Main analytical approach

Baseline characteristics and outcomes will be described using counts and relative frequencies for categorical variables and means, standard deviations, medians, minimums, maximums, and quartiles 1 and 3 for continuous variables. For event outcomes, incidence rates will be estimated using unadjusted Poisson regression, accounting for person-time since index (i.e., first CAB+RPV LA injection) where appropriate. Additional analytic approaches may also be considered for select time-to-event outcomes (e.g., time to discontinuation) such as estimators that take into account

right-censoring (e.g., Kaplan-Meier estimator) and multivariable models such as logistic regression as applicable.

Analyses will be stratified by BMI (< 30, ≥ 30-40 and ≥40 kg/m^2), age (18-49, 50-64, ≥ 65 years), sex (male, female), race/ethnicity, sex/race, and country at first CAB+RPV LA injections, as sample size allows, to assess characteristics, adherence, persistence, discontinuation, and virologic effectiveness. Other demographic and clinical variables may also be considered for stratification, if relevant.

Additionally, factors such as, age, sex assigned at birth, race, geographic region, BMI, injection drug use (IDU), CD4 count, history of AIDS-defining events, core class in prior regimen and comorbidities associated with CVF will be explored using a logistic regression model.

The number and proportion of participants with history of resistance to INSTI or NNRTI and individual ARTs and the results of any historical resistance testing will be assessed. Similarly number and proportion of participants with discontinuation/CVF will be assessed for resistance testing and specific INSTI and/or NNRTI RAMs will be described. Subsequent regimen after discontinuation/CVF and virologic outcomes will be described.

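### The 1.28% to 2.13% interval widths in Section 7.5 assume independent participants, but recruitment is by selected sites, so they are a best case rather than an expected result

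*Protocol*

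**What the plan says.** Section 7.5 gives the target: "The study will aim to enroll up to approximately 2,000 participants". It adds that "There is no formal statistical hypothesis to be tested in these analyses", so the size is justified by precision alone. The precision was computed "using the exact Clopper-Pearson method based on the cumulative probabilities of the binomial distribution for 1 proportion", and the result is stated without qualification: "With 2,000 participants, the 2-sided 95% confidence interval precision width for the estimation of virologic failure rate will range from 1.28% and 2.13" per cent, "for a failure rate ranging from 2% to 6" per cent. Table 1 prints the same calculation for sample sizes from 250 to 2,000. The section mentions no number of sites, ICC or design effect, and does not state that independence is assumed.

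Recruitment is through sites. Section 7.2 takes participants from participating clinical sites in several countries, twelve of them anticipated. On the choice of sites it says "The study will aim to select a diverse group of medical practices to represent diversity in clinical practice settings". Within a site, participants are taken at scheduled visits, by a sampling scheme specific to the site, or in full. Section 7.1 narrows the choice further: "the study will include only the clinical sites that conduct resistance and subtype testing as standard of care". It also leaves treatment and laboratory decisions to the treating physician under standard practice.

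For analysis, Section 7.7.1.1 says "incidence rates will be estimated using unadjusted Poisson regression, accounting for person-time since index". It adds a logistic model for CVF whose listed factors include geographic region but not site. It names no method for confidence intervals or variances. Section 7.7.1.3 plans no sensitivity analyses.

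**The concern.** An exact binomial interval treats 2,000 participants as 2,000 independent pieces of information. If participants at the same clinic resemble each other more than participants at different clinics, the sample carries less information and an honest interval is wider.

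The outcome definitions in Section 7.3.2 give reason to expect some resemblance. Adherence is an injection within 7 days of its target date, which depends partly on clinic scheduling and recall. Discontinuation includes a switch or stop confirmed by the physician. CVF is either two consecutive viral loads of at least 200 copies/mL, which depends on retesting, or one such value followed by discontinuation within 4 months, which depends on a treatment decision. Practices are also chosen for their diversity, and Section 7.9 accepts that the study reflects practice at varied sites.

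This matters because interval width is the only justification given for the sample size. A reader who takes the printed widths as the precision to be achieved may believe the failure rate will be known more exactly than it will be.

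**Working it through.** **Inputs from the Protocol (Section 7.5):** N = 2,000; two-sided 95% exact interval; CVF of 2% and 6%; stated widths 1.28% and 2.13%.

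**Assumptions, because the Protocol gives no figures:** 50, 100 or 200 sites of equal size (m = 40, 20 or 10 participants each); ICC of 0.005, 0.01 or 0.02.

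**Step 1: reproduce the stated figures.** With x = N × P, the lower limit is the 0.025 quantile of Beta(x, N − x + 1) and the upper limit is the 0.975 quantile of Beta(x + 1, N − x).
- P = 0.02, x = 40: 0.0143 to 0.0271, width 0.0128.
- P = 0.06, x = 120: 0.0500 to 0.0713, width 0.0213.

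All 40 widths in Table 1 reproduce to within 0.0001. There is no arithmetic error.

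**Step 2: allow for site.** Design effect DE = 1 + (m − 1) × ICC; effective N = 2,000 / DE; then the exact width at the effective N. For 50 sites and ICC 0.01, DE = 1 + 39 × 0.01 = 1.39 and effective N = 2,000 / 1.39 = 1,439.

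| Sites (m) | ICC | DE | Effective N | Width at 2% | Width at 6% |
|---|---|---|---|---|---|
| any | 0 | 1.000 | 2,000 | 1.28% | 2.13% |
| 200 (10) | 0.005 | 1.045 | 1,914 | 1.31% | 2.18% |
| 200 (10) | 0.01 | 1.090 | 1,835 | 1.34% | 2.23% |
| 200 (10) | 0.02 | 1.180 | 1,695 | 1.40% | 2.32% |
| 100 (20) | 0.005 | 1.095 | 1,826 | 1.34% | 2.23% |
| 100 (20) | 0.01 | 1.190 | 1,681 | 1.40% | 2.33% |
| 100 (20) | 0.02 | 1.380 | 1,449 | 1.52% | 2.52% |
| 50 (40) | 0.005 | 1.195 | 1,674 | 1.41% | 2.34% |
| 50 (40) | 0.01 | 1.390 | 1,439 | 1.52% | 2.53% |
| 50 (40) | 0.02 | 1.780 | 1,124 | 1.74% | 2.87% |

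**Step 3: what an interval that ignores site would cover.** In beta-binomial simulations at 6% CVF, the nominal 95% interval covers about 93% (100 sites) and 91% (50 sites) at ICC 0.01, and about 91% and 85% to 86% at ICC 0.02. At ICC 0 it covers at least 95%.

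**Step 4: is the ICC range credible for a rare endpoint?** In a beta-binomial model the between-site SD of the true risk is √(ICC × P × (1 − P)). At P = 0.02, P(1 − P) = 0.0196:
- ICC 0.005: √0.000098 = 0.0099, or 1.0 percentage point.
- ICC 0.02: √0.000392 = 0.0198, or 2.0 points, as large as the mean itself.
- ICC 0.05: √0.00098 = 0.0313, or 3.1 points around a mean of 2 points.

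The last is hard to believe for CVF, so the range stops at 0.02, which is already demanding at 2% CVF.

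**The case against.** The strongest reply has four parts.

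- **The figures are right and the method is named.** This stands. Section 7.5 also sets no precision target that could be missed. The objection is only to presenting the best case as the result, with the independence assumption unstated.
- **The size rests on assumed inputs.** This also stands. With 200 sites and ICC 0.005 the widths are 1.31% and 2.18%, which is immaterial. An ICC of 0.05 with 50 sites would give 2.27% and 3.73%, but Step 4 shows how extreme that is for a 2% endpoint, and the conclusion does not rest on it.
- **Sites may be regarded as fixed.** If the estimate describes only participants at the participating sites, between-site differences do not inflate its variance and the binomial interval is adequate. This is a fair limit on the point. It does not help a reader who wants to generalise, and Section 7.2 aims for practices that represent diversity in clinical settings.
- **The analysis variance may be left to the analysis plan.** A reader might infer that the planned intervals are themselves too narrow. The Protocol does not show that. Section 7.7 names no interval or variance method, an unadjusted Poisson model means one without covariates rather than one without robust errors, and an analysis plan not at hand may allow for site. That plan could not, however, alter what Section 7.5 already asserts about precision.

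Two smaller points: the practice-selection sentence is printed under the retrospective participants, although its wording is general, and country stratification is planned where numbers allow. Neither removes the clustering, since Section 7.2 recruits everyone through participating sites.

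**Conclusion.** The point holds in limited form. Section 7.5 states as fact a precision that applies only to independent participants, while Sections 7.1 and 7.2 describe recruitment within selected practices, and nothing in the Protocol allows for that or states the assumption. For inference beyond the participating sites, the widths of 1.28% and 2.13% are a best case. Under the assumed 50 to 200 equal sites and ICC of 0.005 to 0.02, they become about 1.3% to 1.7% at 2% CVF and 2.2% to 2.9% at 6% CVF. At worst in that range the width grows by about a third (1.74 / 1.28 = 1.36; 2.87 / 2.13 = 1.35). With an ICC near zero, or many small sites, almost nothing changes.

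Table 1 is not miscalculated, and the Protocol does not establish that the reported intervals will be too narrow, only that they would be if computed without allowance for site. The sample size need not change. The correction is worth making because these widths are the only stated support for 2,000 participants.

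**What to change.** - **Section 7.5:** state that Table 1 assumes independent participants with no within-site correlation. Give the expected number of sites and the widths at 2,000 over a stated design-effect range, for example 1.0 to 1.8. That runs from 1.28% to about 1.7% at 2% CVF and from 2.13% to about 2.9% at 6% CVF.
- **Section 7.7.1.1:** specify that confidence intervals for proportions, Poisson rates and Kaplan-Meier estimates, and the standard errors of the CVF logistic model, use site as the cluster (cluster-robust variance or a site-level bootstrap). For CVF, where events are few, use an exact interval on the effective sample size, that is, the observed N divided by the estimated design effect.

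The cost is about one sentence in each section. Sites enter the data themselves, so site should be available for every participant, and the variance methods are standard software options. The downside is somewhat wider stated and reported intervals. Enrolment and data collection are unaffected.

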**Table 1. Exact Confidence Intervals for Various Combinations of Sample Size and Proportions**

Confidence level	Sample size (N)	Proportion (P)	95% Lower limit	95% Upper limit	Actual width
0.95	250	0.0200	0.0065	0.0461	0.0395
	250	0.0300	0.0126	0.0595	0.0469
	250	0.0400	0.0193	0.0723	0.0530
	250	0.0500	0.0265	0.0848	0.0583
	250	0.0600	0.0340	0.0970	0.0631
	500	0.0200	0.0096	0.0365	0.0268
	500	0.0300	0.0169	0.0490	0.0321
	500	0.0400	0.0246	0.0611	0.0365
	500	0.0500	0.0326	0.0729	0.0403
	500	0.0600	0.0408	0.0846	0.0437
	750	0.0200	0.0112	0.0328	0.0215
	750	0.0300	0.0190	0.0449	0.0259
	750	0.0400	0.0271	0.0566	0.0295
	750	0.0500	0.0355	0.0681	0.0326
	750	0.0600	0.0441	0.0795	0.0354
	1,000	0.0200	0.0123	0.0307	0.0185
	1,000	0.0300	0.0203	0.0426	0.0222
	1,000	0.0400	0.0287	0.0541	0.0253
	1,000	0.0500	0.0373	0.0654	0.0281
	1,000	0.0600	0.0461	0.0766	0.0305
	1,250	0.0200	0.0130	0.0294	0.0164
	1,250	0.0300	0.0213	0.0410	0.0198
	1,250	0.0400	0.0298	0.0524	0.0226
	1,250	0.0500	0.0386	0.0636	0.0250
	1,250	0.0600	0.0475	0.0746	0.0272
	1,500	0.0200	0.0135	0.0284	0.0149
	1,500	0.0300	0.0220	0.0399	0.0180
	1,500	0.0400	0.0307	0.0512	0.0205
	1,500	0.0500	0.0395	0.0623	0.0228
	1,500	0.0600	0.0485	0.0732	0.0247
1,750	0.0200	0.0140	0.0277	0.0137	
1,750	0.0300	0.0225	0.0391	0.0166	
1,750	0.0400	0.0313	0.0503	0.0190	
1,750	0.0500	0.0403	0.0613	0.0210	
1,750	0.0600	0.0493	0.0722	0.0228	
2,000	0.0200	0.0143	0.0271	0.0128	

Confidence level	Sample size (N)	Proportion (P)	95% Lower limit	95% Upper limit	Actual width
	2,000	0.0300	0.0230	0.0385	0.0155
	2,000	0.0400	0.0318	0.0495	0.0177
	2,000	0.0500	0.0409	0.0605	0.0196
	2,000	0.0600	0.0500	0.0713	0.0213

## 7.6. Data Management

The Qualtrics electronic data capture (EDC) system will be used to capture data from eCRFs and participant surveys. The system will be programmed and tested by RTI-HS data management staff. Participants who consent and are formally enrolled in the study will be asked to complete the baseline survey on a tablet provided to sites by RTI-HS while at the clinical site and the month 12 follow-up survey either on their own device via an electronic link provided by RTI-HS or on a tablet provided to sites by RTI-HS. If participants skip a question, they will be prompted to complete it. If they still wish to skip it, they will be able to continue to the next question. Investigators or authorized staff will enter clinical data from participants' medical records directly into the EDC system at the protocol specified timepoints. There is no plan to reconcile any discrepancies in data between individual responses to the survey and their medical record data.

Data will be linked by a common participant identification (ID) code (i.e., participant data are de-identified). Limited personal IDs (e.g., age but not names or email addresses) will be stored with the data.

All data management activities will be fully documented in a detailed data management plan. The plan will describe the EDC system used in the study, user acceptance testing of the system, data sources, data collection/entry methods, querying of missing or unclear data, data cleaning plans, data storage procedures during the study, data set creation, database lock, and data archival. Data from this study may be utilized to compare to outcomes among individuals on other ARV regimens collected as part of other protocols or studies.

